10.2 Analysis Sets

The analysis sets are:

- Intention-to-treat (ITT) population: all randomised subjects who received at least one dose of IMP.
- Primary population for Part 1 primary endpoint and Part 2 combination rule endpoint for Alternative Scenario: Per protocol (PP) for nodulectomy at 6 months (ND6M), i.e. all ITT subjects who had Month 6 nodulectomy with live female adult worms, who completed treatment and who did not take prohibited medication during the study (see Appendix 8 Sections II and IV).
- Primary population for Part 2 proportion of subjects with microfilaria depletion at Month 24 endpoint: PP population for microfilaria, defined as all subjects in the ITT population who had microfilaria-positive skin-snips at baseline, who completed treatment, had skin snips at Month 24 or received ivermectin rescue before Month 24, and who did not take prohibited medication during the study (see Appendix 8 Sections II and IV).
- Primary population for Part 2 secondary endpoints 2a: PP population for nodulectomy at 24 months (ND24M), i.e. all ITT subjects who had Month 24 nodulectomy with female adult worms, who completed treatment and who did not take prohibited medication during the study.
- Primary population for Part 2 secondary endpoints 2b: PP population for nodulectomy at 24 months (ND24M) with live female adult worms, i.e. all ITT subjects who had Month 24 nodulectomy with live female adult worms, who completed treatment and who did not take prohibited medication during the study.
- Safety population: all randomised subjects who received at least one dose of IMP.

Subjects who take prohibited medications that may have an impact on the study objectives (Appendix 8- sections II and IV) are excluded from the PP populations. Specifically subjects who take medications with an anti-filarial or anti-Wolbachia effect at any time during the study (Appendix 8-section II) or strong CYP3A inducers or dexamethasone during the treatment period that may lower ABBV-4083 or albendazole exposures (see Appendix 8 - Section IV) are excluded from the PP population.

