10.4 Handling of Potential Intercurrent Events for the Primary and Key Secondary Endpoints

Subjects who do not complete the treatment as defined above will be excluded from the PP populations (but will be included in the ITT analyses). Subjects in Part 2 with evidence of reinfection will be included in all analyses as it is not possible to distinguish between reinfection and a failure in this study. However, in sensitivity analyses, those subjects will be excluded from efficacy analysis. Subjects in Part 2 who do not have skin snips at Month 24 will be excluded from the PP for microfilaria population, except those who received ivermectin rescue before Month 24. Any subject who received ivermectin rescue before Month 24 as allowed per protocol will be counted as a failure in both the PP and ITT analyses of the Part 2 primary and key secondary endpoints. Subjects who do not have nodulectomy data at Month 6 (for Part 1 and for Part 2 Alternate Scenario) or Month 24 (for Part 2) will be excluded from the PP for the ND6M or ND24M populations, respectively. Subjects who take prohibited medications (see Appendix 8-sections II and IV) will be excluded from the PP analyses; subjects who take medications with an anti-filarial or anti-Wolbachia effect at any time during the study (see Appendix 8 - Section II) will be counted as failures in the ITT analyses.

In the ITT analysis of the primary and key secondary endpoints, if the result is missing for the assessment, the assessment of that outcome will be a failure if the absence of data is due to administration of prohibited medication or withdrawal due to efficacy or safety issue. In the event of withdrawal of informed consent, subject lost to follow-up or withdrawal for a reason independent from the treatment (e.g. moving, lethal accident), multiple imputation will be used to impute the missing data.

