- 19. AE collection from signature of Informed Consent onwards. AE monitoring will be performed as specified in Section 9.3.4 and will include scheduled questioning at the indicated time-points.
- 20. In the event of certain AEs considered to be associated with the IMP, additional examinations may be conducted in order to better interpret the AE, including safety laboratory, PK, ophthalmological, physical, neurological, and parasitological (eye and skin) examinations.
- 21. Blood samples for dry blood spot assay (PK) of ABBV-4083 and albendazole sulfoxide will be collected on Day 0: 0h (any time before dosing), 1h, 2h, 3h, 4h, 6h and 12h (+/- 15 minutes for all); and Day 1 at 0h (up to 30 min prior dosing). Samples on Day 3, 6 and 13 will be collected between 2 and 4 hours after dosing.
- 22. Blood and urine samples will be collected at the time-points indicated and stored for future analysis (for example: biomarkers, immunological markers testing). Note: in addition, where feasible, tissue samples collected from other procedures during the study (e.g. skin, nodules etc.) will also be stored after analysis. Subjects have the possibility to opt out of exploratory samples.
- 23. Nodulectomy must be conducted only after completion of the procedures at the Month 6 visit.
- 24. In-house Period will have one additional day on D13 for observation post last dose and to perform pregnancy test at the end of exposure period.

Confidential Page 99 of 112

- 25. Post-nodulectomy wound care will continue for up to approx. 2 weeks. The subject may go back to the community or may stay at the investigational site for logistic reasons or if medically indicated. End of Study visit will be 2 weeks after nodulectomy +/- 2 weeks. The visit may be performed in the community.
- * Repeat period can be extended to 7 days in exceptional circumstances, with prior agreement of the Sponsor (exception of pregnancy test which must be repeated within 2 days and can be urine if serum test was already done)

Confidential Page 100 of 112

Appendix 2. Schedule of Events in Part 2

Table 8. Schedule of Events in Part 2

All study days / times are calculated relative to the time of administration of IMP on Day 0, i.e. 0d00h00m.

Time (and minders if	Time (and window, if Screening ¹ In-house			e	Out-patient							

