## 4.0 Analysis Populations

The following population sets will be used for the analyses.

The Intention-to-Treat (ITT) population includes all randomised subjects who received at least one dose of study drug. The ITT population will be used for all non-primary efficacy estimands. Subjects will be included in the analysis according to the treatment arm to which they were randomised.

The Per-Protocol (PP) population will include all ITT subjects who had Month 6 nodulectomy (ND6M) with live female adult worms, who completed treatment and did not take prohibited medication(s) during the study. Treatment completion is defined as taking at least 6 out of 7 days of ABBV-4083 in Arm A, 12 out of 14 days of ABBV-4083 in Arm B, 6 out of 7 days of ABBV-4083 + albendazole in Arm C, 6 out of 7 days of ABBV-4083 and all 3 days of albendazole in Arm D, and 6 out of 7 days of albendazole in Arm E. Prohibited medications (Appendix B) include those with anti-filarial or anti-*Wolbachia* effect taken at any time during the study, or strong CYP3A inducers or dexamethasone taken during the treatment period. The PP population will be used as the primary population for testing the two primary hypotheses (Section 2.1).

The Safety population includes all randomized subjects who received at least one dose of study drug. Subjects will be included in the analysis according to treatment as randomized. The Safety population is the same as the ITT population.

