#### 9.2 Handling of Missing Data for the Primary Endpoint

First, subjects with no count of live female adult worms (no ND6M results or no live female adult worms in the ND6M results) will be excluded from the PP population and the ITT population analysis, because the primary endpoint is a worm-level endpoint about the *Wolbachia* status of a live female adult worm in the ND6M results.

Then, if a subject took prohibited medications with an anti-filarial or anti-*Wolbachia* effect (Appendix B) at any time during the study, all live female adult worms in that subject will be counted as having *Wolbachia* for the ITT population analyses, regardless of the observed *Wolbachia* status. All worms in such subjects will be excluded according to the definition of the PP population (Section 4.0).

Then, if a subject withdrew due to a safety issue (Section 8.0), all the live female adult worms that have missing *Wolbachia* status will be imputed as having *Wolbachia* for both

the PP population and the ITT population analyses. Any live female adult worm that has the observed *Wolbachia* status will be analyzed as observed.

Finally, if any live female adult worm still has missing *Wolbachia* status, the *Wolbachia* status will be imputed for the worms of those subjects in the ITT population analyses using the multiple imputation described below, but those worms will be excluded from the analyses for the PP population.

For multiple imputation, the missing *Wolbachia* depletion results will be generated in 30 datasets in SAS PROC MI (fully conditional specification). The logistic regression method will be used to impute the binary primary *Wolbachia* status for each live female adult worm with missing *Wolbachia* status. The imputation model will include treatment and the randomization stratification factor (Section 2.3) as covariates. The random seed for PROC MI will be the SAS numerical form of the first subject randomization date in the study. In case of non-convergence, the random seed will be updated by adding 100,000 at each attempt until convergence of model occurs. If the model will not converge due to data sparsity issue, the randomization stratification factor will be removed from the imputation model. The primary endpoint data from the 30 datasets will then be separately analyzed using the method described in Section 9.3.1. The results will be combined using SAS PROC MIANALYZE to generate the final inference.

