#### Appendix B. List of Prohibited Medications

The following medications are prohibited throughout the entire study because of their anti-filarial or anti-Wolbachia effects:

- ivermectin (excluding protocol-defined, post-study ivermectin mentioned in Section 2.2)
- moxidectin,
- doxycycline,
- minocycline,
- rifampicin,
- rifapentine.

The following medications are prohibited during the treatment period, up to 24 hours after the final dose.

- Any CYP3A and/or P-gp inhibitors or inducers, such as:
  - rifampicin,
  - phenytoin,
  - phenobarbital,
  - carbamazepine,
  - others known to interfere with the CYP3A and/or P-gp metabolic pathways (the US FDA tables of Substrates, Inhibitors and Inducers will be used as a reference, and included in the Study Operations Manual for reference).
- Dexamethasone is known to interact with albendazole and will also be prohibited during the treatment period, up to 24 hours after the final dose.

Any subject who takes a prohibited medication during the study will be documented via a protocol deviation, which will be used to determine eligibility for the per-protocol population.

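### The antifilarial/anti-Wolbachia drug rule has no cut-off at the measurement, so a drug first taken after the sample was collected still removes the subject from PP and recodes observed results as failures in ITT

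*SAP*

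**What the plan says.** **Part 1.** SAP 4.0 defines the prohibited drugs that matter for PP as those with an antifilarial or anti-Wolbachia effect "taken at any time during the study, or strong CYP3A inducers or dexamethasone taken during the treatment period". SAP 9.2 then sets the consequence in ITT: "at any time during the study, all live female adult worms in that subject will be counted as having" Wolbachia, overriding the observed status. For PP it adds "All worms in such subjects will be excluded according to the definition of the PP population (Section 4.0"). SAP 8.0 repeats both rules. SAP Appendix B opens its list with "The following medications are prohibited throughout the entire study because of their anti-filarial or anti-Wolbachia effects". The only exemption there is "ivermectin (excluding protocol-defined, post-study ivermectin mentioned in Section 2.2"). Appendix B also has PP eligibility follow from the recorded protocol deviation, without a date test.

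**Both parts.** Protocol 10.2 defines the Month 6 nodulectomy (ND6M) PP set as those in the ITT population "who had Month 6 nodulectomy with live female adult worms, who completed treatment and who did not take prohibited medication during the study". That set serves both the Part 1 primary endpoint and the Part 2 combination-rule endpoint. The Part 2 microfilaria set and the Month 24 nodulectomy sets carry the same undated condition. Protocol 10.4, on drugs that act on filariae or Wolbachia, says that anyone taking a drug with such an "effect at any time during the study (see Appendix 8 - Section II) will be counted as failures in the ITT analyses". Appendix 8 footnote a says the same.

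**When the study ends.** Protocol 3.4 makes the End of Study visit part of a subject's participation. For Part 1, Appendix 1 footnote 25 says "End of Study visit will be 2 weeks after nodulectomy +/- 2 weeks". In Part 2 that visit is 2 weeks after the Month 24 nodulectomy (Appendix 2 footnote 25).

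**The concern.** The rule exists to stop a non-study drug from contaminating the endpoint. A drug started after a nodule has been excised, or after the skin snips have been taken, cannot do that. With no cut-off at the procedure, the text still tells the programmer to delete that subject from the primary population and, in ITT, to replace observed clearance with failure.

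The plan behaves differently elsewhere. Protocol 10.2 and 10.4 date the parallel rescue-ivermectin rule: it applies to rescue before Month 24. For safety withdrawals, SAP 9.2 keeps observed worm results and imputes only the missing ones. The prohibited-drug rule alone overwrites observed data, with no date limit.

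At stake are valid results lost from a primary analysis of about 25 subjects per arm in Part 1, or about 17 per arm at Month 6 in Part 2, and an ITT analysis in which a single recoded subject visibly moves the odds ratio.

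**Working it through.** **Length of the exposed window**

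- Part 1: the End of Study visit is 2 weeks after nodulectomy, give or take 2, so 2 − 2 = 0 to 2 + 2 = 4 weeks.
- Part 2, Month 24 skin and nodule endpoints: about 2 weeks.
- Part 2 Alternate Scenario, Month 6 worms: Month 6 to Month 24 is 18 months, and 18/24 = 75% of the window follows the endpoint.

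**Reproducing the planned power (Part 1)**

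Inputs from SAP 2.4: 1 to 10 worms per subject with the stated probabilities (mean 3.79), ICC 0.54 in the 70% and 30% arms, ICC 0.01 in the 90% arm, 2-sided α 0.10. Worm results were simulated as beta-binomial and tested with a marginal logistic model and robust Wald test.

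| Comparison | Stated | One common pairwise odds ratio (4,000 runs) | Arm-specific exchangeable (20,000 runs) | Independence (20,000 runs) |
|---|---|---|---|---|
| 90% v 70%, 25 per arm | 81% | 82.8% | 83.8% | 81.4% |
| 70% v 30%, 17 per arm | 88% | 88.2% | 89.4% | 82.9% |

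The common-odds-ratio fit is within 2 points of both stated figures. Enrolment also agrees: 25/(1 − 0.17) = 30.1, planned as 30.

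**Part 1, primary PP analysis, C v A**

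Assumption: one subject per arm is lost (24 per arm). Power goes from 82.8% to 80.8% in the common-odds-ratio fit, from 83.8% to 82.5% in the arm-specific fit and from 81.4% to 80.0% under independence. The cost is about 1 to 2 points.

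**Part 1, supplementary ITT analysis, C v A**

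Assumption: one of 25 subjects in an arm is recoded to all-failure, so that arm's cleared proportion is multiplied by 24/25.

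- Planned: (0.90/0.10) / (0.70/0.30) = 3.86.
- One in Arm C: 0.90 × 24/25 = 0.864; (0.864/0.136) / (0.70/0.30) = 2.72.
- One in Arm A: 0.70 × 24/25 = 0.672; (0.90/0.10) / (0.672/0.328) = 4.39.
- One in each: (0.864/0.136) / (0.672/0.328) = 3.10.

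Simulated ITT power (common-odds-ratio fit) is 59.7% with one Arm C subject recoded and 68.8% with one in each arm, against 82.8%.

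**Part 2 Alternate Scenario, Month 6 PP set**

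Protocol 10.3.2 assumes 17% drop-out and at least 25% of retained subjects with more than one nodule site: 84 × 0.83 × 0.25 = 17.4, that is 17 per arm. If 5%, 10% or 20% (assumed) took a listed drug for the first time after Month 6, 17 would become 16.2, 15.3 or 13.6.

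**Is such use plausible in Part 2?**

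Exclusion criterion 5 concerns ivermectin need only in the first 6 months. Protocol 2.1 describes ivermectin mass drug administration (MDA) in endemic communities every 6 or 12 months. Appendix 8 Section II exempts post-study and rescue ivermectin, not an MDA dose. An MDA dose at Month 14 would therefore remove a Month 6 histology result. At Month 24, protocol 8.4 gives post-study ivermectin to microfilaria-positive subjects and advises everyone to continue with MDA. A cleared subject who took an MDA dose before the End of Study visit is not clearly exempt.

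**The case against.** **Part 1 exposure is slight.** This stands. Post-study ivermectin, the one listed drug that every Part 1 subject is due after nodulectomy, is exempt. A reader might infer that the rule catches everyone; it does not. Other medication needs the investigator's approval (protocol 8.1), and nothing suggests that doxycycline, minocycline or rifampicin is used in wound care. CYP3A inducers and dexamethasone count only in the treatment period.

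**Part 1 may be read as ending at Month 6.** Protocol 3.1 and SAP 2.2 speak that way, and ivermectin after nodulectomy is called post-study. This makes the Part 1 window partly ambiguous, but protocol 3.4 includes the End of Study visit. The reading does nothing for the Month 6 endpoint in Part 2.

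**The large odds-ratio shifts are ITT.** This stands. ITT is supplementary in Part 1, and the primary PP analysis loses only 1 to 2 points of power per subject lost in each arm.

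**Part 2 is conditional and its SAP is separate.** This stands. Month 6 nodulectomy occurs only in the Alternate Scenario. Protocol 10.5 specifies that endpoint in the PP ND6M set and combines p-values from both parts, so the 18-month window affects only the Part 2 stage. A reader might assume an ITT recoding there too. Protocol 10.6 promises ITT for primary and key secondary endpoints, protocol 5.4 calls this one additional, and protocol 10.7 calls it primary. No ITT effect can be claimed as settled.

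**Bias towards the active arm.** A reader might infer this if poorly responding subjects take more ivermectin later. The documents do not support it. Ivermectin for worsening signs or rising microfilariae is rescue, which the protocol exempts, and the Alternate Scenario has no untreated arm. Nor does the text show that Month 6 set membership would vary with the analysis date, since no repeated combination-rule analysis is planned.

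**Conclusion.** The defect is real and limited. No passage in either document stops the PP-exclusion or ITT-failure rule at the measurement. Followed literally, it discards or overwrites valid results because of drugs that could not have acted on the sample.

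The expected effect in Part 1 is small: a 0 to 4 week window, and about 2 points of PP power at most in these fits if one subject per arm is affected. The supplementary ITT analysis is more sensitive and can move either way (odds ratio 2.72 or 4.39 against 3.86 for one recoded subject in Arm C or Arm A). The greater exposure is the Part 2 Alternate Scenario Month 6 endpoint, with about 75% of the window after the endpoint. The Month 24 per-subject skin endpoint and the Month 24 nodule endpoints are exposed for about 2 weeks.

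All counts and rates of drug use are assumptions, because the documents give none. How the Part 2 SAP will handle the rule cannot be judged from the documents supplied.

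**What to change.** In SAP 4.0, 8.0 and 9.2, and in protocol 10.2, 10.4 and Appendix 8 footnote a, change only the analysis consequence. A listed antifilarial or anti-Wolbachia drug should count for PP exclusion or ITT failure only if it was started on or before the date of the procedure that measures the endpoint in question: Month 6 nodulectomy, Month 24 skin snips or Month 24 nodulectomy. Apply the test separately for each endpoint, and analyse results measured before the drug was started as observed. Carry the rule into the Part 2 SAP.

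Leave the whole-study prohibition and the recording of protocol deviations in SAP Appendix B and protocol Appendix 8 as they are. Only the Appendix B sentence that derives PP eligibility from the deviation should point to the dated rule. State a convention for incomplete medication start dates.

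While these passages are open, reconcile the exemptions: SAP Appendix B lists post-study ivermectin only, whereas protocol Appendix 8 also lists rescue ivermectin.

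The cost is text edits and a comparison of two dates already collected. Drugs started before the measurement still trigger the rule, so no protection is lost.

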#### 2.4 Sample Size Determination

To test the primary hypothesis for the proof of concept, an alternating logistic regression will be used to compare the proportion of live female adult worms without *Wolbachia* at Month 6 between each of the four active arms (Arm A, B, C, or D) and the control arm (Arm E), taking into account the clustering of this worm-level endpoint by subject. Using simulations that add substantial clustering by subject to the endpoint values and assuming the number of worms in each subject varies from 1 to 10, following the multinomial distribution with probability = (0.20, 0.16, 0.16, 0.16, 0.08, 0.08, 0.08, 0.03, 0.03, 0.02) for values (1, 2, 3, 4, 5, 6, 7, 8, 9, 10), 17 subjects will provide 88% power to detect the difference between an active arm (Arm A, B, C, or D) where 70% of worms are without *Wolbachia* (2-sided  $\alpha = 0.10$ ). The clustering of the endpoint values by subject is provided by the Pearson intraclass correlation coefficient (ICC) for binary outcomes and was given as ICC = 0.54 for simulated arms where 70% or 30% of the worms are without *Wolbachia*.

To test the primary hypothesis for the combination rule, an alternating logistic regression will be used to compare the proportion of live female adult worms without *Wolbachia* at Month 6 between the combination arm (Arm C or D) and the two single drug arms (Arm A and E) separately, 25 subjects per arm will provide 81% power to detect the difference between the combination arm where 90% of worms are without *Wolbachia* and the single drug arm where 70% of worms are without *Wolbachia* (2-sided  $\alpha = 0.10$ ). ICC = 0.54 was added to the simulated arm where 70% of the worms are without *Wolbachia*. Minimal clustering (ICC = 0.01) was added to the simulated arm where 90% of the simulated arm where 90% of the worms are without *Wolbachia* because there would be little variation among subjects with an overall high response rate. 30 subjects will be enrolled per arm to account for 17% drop out by Month 6.

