#### 9.3.2 Main Analysis of Primary Efficacy Endpoint

The primary efficacy endpoint will be compared between the following pairs of treatment arms for the PP population in Part 1:

- For proof of concept: (1) A vs. E, (2) B vs. E, (3) C vs. E, (4) D vs. E;
- For satisfying the combination rule: if Arm C is to advance to Study B18-894/DNDi-TYL-01 Part 2, then (1) C vs. A, (2) C vs. E; if Arm D is to advance to Part 2 but Arm C is not, then: (1) D vs. A, (2) D vs. E.

The comparisons will be conducted using contrasts from an alternating logistic regression model that includes all the five treatment arms as factors. The alternating logistic regression will account for within-subject association of the worm-level endpoint by estimating the pairwise log odds ratio (different than the odds ratio of the primary estimand) of a worm's Wolbachia status in relation to another worm's Wolbachia status within each subject. In this regression model, the within-subject association is estimated with one parameter. That is, the pairwise log odds ratios used to account for the within-subject association are assumed as equal for all pairs of worms within a subject, and the same log odds ratios are assumed for all subjects in the same treatment arm. However, different log odds ratios/parameters are assumed in different treatment arms, allowing for arm-specific within-subject associations. If the model does not converge, the within-subject associations for the five treatment arms will be assumed as the same. If the model still does not converge, a generalized linear mixed model will be used instead of the alternating logistic regression model. The mixed model will assume the framework of a logistic regression using a random intercept for each subject to account for the within-subject association of the worm-level endpoint. The variance of the random intercepts will be assumed as different for the five treatment arms.

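### The ITT imputation draws each worm's missing Wolbachia status without regard to the subject it came from, so the supplementary ITT standard error is understated, increasingly so as missingness grows

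*SAP*

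**What the plan says.** SAP 9.2 handles missing data in a fixed order.

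1. Subjects with no nodulectomy result, or no live female worms in it, leave both the PP and the ITT analysis.
2. For ITT, all worms of subjects who took anti-filarial or anti-*Wolbachia* drugs count as failures.
3. Missing worms of subjects who withdrew for a safety reason count as failures.
4. Worms still without a status are dropped from PP and multiply imputed for ITT, in 30 datasets pooled by PROC MIANALYZE.

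On the imputation model the SAP says: "The imputation model will include treatment and the randomization stratification factor (Section 2.3) as covariates". The stratification factor is one versus more than one operable site. If the data are too sparse, "the randomization stratification factor will be removed from the imputation model", which leaves treatment alone.

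The analysis model in SAP 9.3.2 is of another kind: "The alternating logistic regression will account for within-subject association of the worm-level endpoint by estimating the pairwise log odds ratio" between worms of one subject, with a separate association parameter for each arm. The sample size in SAP 2.4 rests on "ICC = 0.54 for simulated arms where 70% or 30% of the worms are without" *Wolbachia*. For the 90% arm, "Minimal clustering (ICC = 0.01) was added to the simulated arm".

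Protocol 10.4 calls for multiple imputation but gives no model, so SAP 9.2 is the only specification. SAP 9.3.3 describes the ITT repeat as supplementary.

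**The concern.** Under the plan's own assumptions, worms from one subject tend to share a status. The imputation model treats every missing worm as a fresh draw at the arm's rate, whatever was seen in the same subject. The analysis model then reads those draws as independent information. The expected result is an ITT standard error that is too small, intervals that are too narrow and p-values that are too low.

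At stake is how the ITT result reads beside the per-protocol result. The ITT repeat is the only analysis that SAP 9.3.3 lists under sensitivity and supplementary analyses of the primary endpoint. It should not look more precise than its data allow.

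**Working it through.** **Inputs.** From SAP 2.4: ICC 0.54 (70% and 30% arms) and 0.01 (90% arm); worms per subject from 1 to 10 with the stated probabilities, mean 3.79; about 25 evaluable subjects per arm. From SAP 9.1: two-sided alpha 0.10. From SAP 9.2: M = 30 imputations. The share of worms with missing status is in neither document; 0-40% is assumed.

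**The plan's own figure.** Effective worms per arm = n × Σ p_m·m / (1 + (m − 1)·ICC) = 17 × 1.406 = 23.9. A two-proportion calculation at 70% v 30% then gives 88.9% power, and a simulation with beta-binomial worms gives 89.1%. The plan states 88%. A cruder log-odds approximation gives 85%. The simulated data behave like the plan's.

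**What is drawn and what should be drawn.** With clearance rate p and intraclass correlation ρ, a worm is clear with probability p + (1 − p)ρ if a fellow worm is clear, and p(1 − ρ) if it is not.

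- p = 0.70, ρ = 0.54: 0.70 + 0.30 × 0.54 = 0.862, and 0.70 × 0.46 = 0.322. The SAP draws about 0.70 in both cases.
- p = 0.90, ρ = 0.01: 0.90 + 0.10 × 0.01 = 0.901, and 0.90 × 0.99 = 0.891. Here independent draws are nearly right.

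**Lost clustering.** A pair of worms keeps its correlation only if both were observed. With a share f of worms missing at scattered positions, the apparent ICC is about (1 − f)² × 0.54: 0.44 at 10%, 0.35 at 20%, 0.19 at 40%. The simulated values are 0.42, 0.34 and 0.19, from 0.53 with nothing missing.

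**Effect on the standard error.** Log odds ratio, 70% v 30%, ICC 0.54 in both arms, 25 per arm, about 800 trials per setting, missing completely at random. Subject-aware means imputation conditional on the subject's observed worms. Shortfall = 1 − (SAP / subject-aware). Type I error (nominal 10%) comes from runs with equal rates in both arms; a dash means no figure is reported.

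| Missing (assumed) | Pattern | SAP SE | Subject-aware SE | Shortfall | Type I, SAP |
|---|---|---|---|---|---|
| 0% | scattered | 0.522 | 0.522 | 0 | 11.5% |
| 5% | scattered | 0.514 | 0.526 | 2.3% | 13.9% |
| 10% | scattered | 0.511 | 0.532 | 3.9% | 13.8% |
| 20% | scattered | 0.500 | 0.545 | 8.3% | 16.8% |
| 30% | scattered | 0.500 | 0.564 | 11.3% | – |
| 40% | scattered | 0.505 | 0.588 | 14.1% | 17.7% |
| 0% | whole subjects | 0.524 | 0.524 | 0 | 12.2% |
| 5% | whole subjects | 0.524 | 0.538 | 2.6% | – |
| 10% | whole subjects | 0.527 | 0.552 | 4.5% | 13.3% |
| 20% | whole subjects | 0.532 | 0.589 | 9.7% | 16.1% |
| 30% | whole subjects | 0.540 | 0.635 | 15.0% | – |
| 40% | whole subjects | 0.558 | 0.699 | 20.2% | 23.4% |

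Monte Carlo error of the type I figures is about 1.1-1.5 points. Subject-aware imputation stays at about 11-14% throughout.

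**Why.** Pooled variance is T = W + (1 + 1/M)B, and both parts are too small. In the equal-rates run with 40% of whole subjects missing, √W and √B are 0.471 and 0.289 under the SAP, so √T ≈ √(0.222 + 1.033 × 0.0835) = 0.555. Under subject-aware imputation they are 0.529 and 0.452, so √T ≈ √(0.280 + 1.033 × 0.204) = 0.70. The actual spread of the estimate is about 0.81 in both.

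**C v A (90%, ICC 0.01, v 70%, ICC 0.54).** The gap is smaller. SAP against subject-aware at 10% missing: 0.516 v 0.529 scattered and 0.522 v 0.537 whole subjects (2.5% and 2.8% short). At 40%: 0.582 v 0.620 and 0.617 v 0.688 (6.1% and 10.3% short).

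**Second simulation.** With 70% v 70%, 2,500 trials and 10 imputations, 20% scattered missing gives a mean SE of 0.509 against a true SD of 0.598. Coverage of 90% intervals is 83.8%, against 88.2% with cluster-aware imputation. At 10% missing the two are 86.3% and 87.0%.

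**The case against.** The strongest reply is that the imputation touches little. It reaches only worms already counted as live adult females that lack an immunohistology result after the failure rules. A reader might infer that the planned 17% dropout is imputed this way. It is not, because subjects without nodulectomy data leave the ITT analysis as well. Neither document suggests that 20-40% of worms will lack a status. At 5-10% the loss is small, and at 10% it is hard to separate from simulation error. The ITT analysis is supplementary, and protocol 10.9 rests regimen selection on all unblinded data. All of this stands and limits the weight of the point.

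It also stands that part of the undercoverage is not due to imputation. With nothing missing, type I error is already about 12%, from the small-sample robust standard error.

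Calling the ITT repeat the only check on the per-protocol result would go too far. SAP 9.4.2 analyses nodule-level PCR status in ITT on observed data, with clustering by subject.

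The reply does not remove the defect. SAP 8.0 sends to imputation any subject who stopped for treatment-independent reasons and has live worms, even if every status is missing. That is the whole-subject pattern, which has the largest shortfalls in the table. In every pattern with missing data, the SAP's standard error was below the subject-aware one.

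**Conclusion.** The point holds: as specified, the imputation understates the ITT standard error, and the shortfall grows with missingness. With ICC 0.54 in both arms it is about 2-5% at 5-10% of worms missing and about 8-10% at 20%. Type I error at 20% is about 16-17%, some 4-5 points above the level with nothing missing. For C v A the shortfall is smaller.

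A reader might infer that the ITT standard error shrinks as more data go missing. That is not general. It falls only when missing worms are scattered within subjects and both arms have high ICC, and only up to about 20-30% missing (0.522 to 0.500). With whole subjects missing, or for C v A, it does not fall overall but rises too slowly. A reader might also infer that the primary result is compromised. It is not, because the per-protocol analysis drops these worms and uses no multiple imputation.

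The sizes assume statuses missing completely at random, beta-binomial clustering, a 50:50 stratum without effect, and a GEE with exchangeable correlation in place of alternating logistic regression. The direction follows from the SAP text alone; the size depends on a missing share that the documents do not give.

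**What to change.** In SAP 9.2, replace the imputation model with a logistic model that has treatment, stratum and a subject random intercept. Let the intercept variance differ by arm where it can be estimated, and otherwise use a common variance. Each missing worm is then drawn conditional on the subject's observed worms; a subject with none observed gets one drawn intercept shared by all its worms. SAP 9.3.2 already names a random-intercept logistic model with arm-specific variances as its analysis fallback, so the structure is not new to the plan.

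With about 25 subjects per arm and one arm possibly near 90%, convergence may fail. In that case, fit the alternating logistic regression of SAP 9.3.2 to the ITT worms with observed status, and record this in SAP 13.0 as a departure from the multiple imputation in protocol 10.4. In the C v A runs at 20% missing, this gave standard errors close to subject-aware imputation (0.543 v 0.551 scattered, 0.563 v 0.574 whole subjects).

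Report the number of imputed worms and affected subjects by arm. Also correct the cross-reference: SAP 9.2 sends the imputed datasets to Section 9.3.1, which only defines the endpoint; the method is in 9.3.2.

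The cost is SAP wording and a multilevel imputation step in place of the PROC MI call. No new data are needed.
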